2.3 EDC CRF data monitoring and quality management

A backlog of paper CRFs began to be entered into Forte EDC database on 4/20/2020 by PHS staff who had been trained for EDC data entry. That responsibility was transferred back to clinical study staff by the end of April.

Data can be entered directly into Forte EDC as they are collected at clinical sites to ensure a smooth and systematic flow of activities and to avoid backlogs and uneven workloads. Automated validation rules in Forte EDC will catch inconsistent data collection within or across CRFs as the data are entered. Forte EDC offers a user-friendly feature with color coding to reflect data status (data error versus error-free). A data discrepancy alert will also appear when a data element is improperly entered. For example, data element checks will be displayed as

soon as the data are entered into Forte EDC. Similar data validation processes can be implemented using SAS. For this study, both processes will be used.

A specimen ID will be issued once a specimen is collected and documented in both the CRF and specimen tracking databases. Specimen quality will be documented in the specimen tracking database after the specimen is registered in the SQL database at the DCC. Data will be seamlessly and automatically integrated daily to ensure timely data checks and data reports.

CRF Data quality reports will be generated daily and will include: (a) CRF status (missing but expected, incomplete but expected, complete as expected); and (b) data element status (missing, illogical, or invalid values; inconsistencies across CRFs in Forte EDC or using SAS).

The Clinical Site Coordinator will work closely with the DCC Data Coordinator to resolve data discrepancies by directly entering the missing-but-expected CRF or correcting data errors through Forte EDC. Data quality alerts will be generated continuously until resolved.

Prescreening data will be reported daily. The number of subject enrollments will be reported daily when data are available in the DCC central database.

Due to the volume of recruitment, a serious adverse event (SAE) report will be generated and reported to PIs and the DSMB weekly. The DCC has implemented an MOP for central SAE review and reporting process (detailed in a later section).

The DCC will work closely with the Trial PIs, laboratory core, and each site regarding non-compliant specimens, and action will be taken to remedy the issue if possible; the DCC will perform a descriptive analysis to compare specimen quality before and after the problem resolution.

3. Site Training and Management

Site staff training:

The DCC will assist the Trial PIs in the preparation of training materials and will conduct a series of role-specific training sessions for site personnel including the Trial PI, regulatory staff, and clinical coordinators on topics including the study protocol, Forte EDC training for patient scheduling, informed consent, and CRF data collection.

Training in Forte EDC will be performed at two levels: general Forte EDC data-entry training, and study-specific training. This training can be completed through webinars.

On- and Off-Site Visits:

DCC staff will discuss site visit results with the Trial PIs and clinical coordinators at the end of a site visit. An audit report will be written for each visit, listing all findings and requesting resolution. A follow-up meeting or conference call may be needed for clarification. Audit results will be documented by the DCC as part of the Trial Master Files (TMFs). The DCC will maintain close communication with the Trial PIs and Leadership Committee regarding auditing results. If a serious protocol violation occurs, action may be taken, as decided by the PI and DSMB.

4. Safety data collection and reporting

4.1 Adverse event definitions

For this study, the following standard AE definitions are used:

Adverse event: An Adverse Event (AE) is any untoward medical occurrence in a Participant administered an investigational product or undergoing a procedure, which does not necessarily have a causal relationship with the treatment. An AE can be any unfavorable and unintended sign, symptom, or disease temporally associated with the use of an investigational product, whether or not it is related to the investigational product.

Serious Adverse Event: A Serious Adverse Event (SAE) is any AE that results in any of the following outcomes:

- Results in death
- Is life-threatening
- Requires inpatient hospitalization or prolongation of existing hospitalization
- Results in persistent or significant disability/incapacity
- Is a congenital anomaly/birth defect.

AEs are graded according to the following scale:

Mild: An experience that is transient and requires no special treatment or intervention. The experience does not generally interfere with usual daily activities. This includes transient laboratory test alterations.

Moderate: An experience that is alleviated with simple therapeutic treatments. The experience impacts usual daily activities. Includes laboratory test alterations indicating injury, but without long-term risk.

Severe: An experience that requires therapeutic intervention. The experience interrupts usual daily activities. If hospitalization (or prolongation of hospitalization) is required for treatment it becomes an SAE.

The study uses the following AE attribution scale:

Not related: The AE is clearly not related to the study drug (i.e., another cause of the event is most plausible, and/or a clinically plausible temporal sequence is inconsistent with the onset of the event).

Possibly related: An event that follows a reasonable temporal sequence from the initiation of study procedures, but that could readily have been produced by a number of other factors.

Related: The AE is clearly related to the study drug.

Each SAE will be reviewed by an independent medical monitor, [name] MD, a rheumatology specialist at HFHS, who is not be involved in the proposed study. The detailed review process is detailed in MOP.

4.2 Safety reporting

All problems having to do with subject safety will be reported by the Principal Investigator (PI) to the IRB within ten working days. Specifically, the following will be reported, in writing: 1) all serious adverse events potentially associated with the study drug, and/or 2) any incidents or problems involving the conduct of the study or patient participation, including problems with the recruitment and/or consent processes. The PI will provide a discussion of any side effects or problems noticed in the course of the study to the IRB.

The DCC will produce safety reports that list serious adverse events, deaths, and disease or treatment specific events, in aggregate, for DSMB weekly meetings or at a scheduled meeting.

The DSMB will review safety reports by blinded treatment group. If there are a significant number of adverse events, the DSMB may request that the treatment groups be unblinded to ensure there are not problematic side effects.

5. Reports for Study Progress and Quality Control

5.1 Study progress Reports

The DCC will produce administrative reports that describe study progress. These reports will be reviewed internally by the DCC and PI for ongoing quality control and will be presented to the Data Safety Monitoring Board (DSMB) at scheduled meetings.

5.2 Subject accrual / randomization Reports

The DCC will produce daily accrual / randomization reports, which will include:

- 1) The number of prospective Participants who completed a Volunteer Survey, and their eligibility, demographics and occupations.
- 2) The number of Participants currently enrolled.

A weekly report to DSMB will include a cumulative report of enrollment and enrollment projection.

5.3 Data collection and management Reports

Data quality will be assessed using measures listed below:

- CRF status by form (overall and by clinical site): the number of CRFs received the number of expected CRFs, and percentage of missing expected CRFs.
- The number of data queries generated and the number/percent of queries resolved (overall and by clinical site).
- Protocol deviations including: 1) number of subjects who were ineligible but randomized into the trial; 2) numbers of subjects who were enrolled but not according to randomization sequence.

5.4 DSMB Reports

A weekly report to DSMB will include 1) Cumulative report of enrollment and projection; 2) AE and SAE report.

Reports for a scheduled DSMB meeting will include the cumulative daily and weekly reports; safety report; and the efficacy results at the interim analysis session.

6. Statistical Analysis Plan (SAP)

A formal SAP will be developed before study completion or database lock for an interim analysis. Statistical issues not addressed in the study protocol will be addressed in the formal SAP.

6.1 Study Design

Participants who meet study entry criteria and are not on HCQ prior to study enrollment will be randomized in a 1:1:1 blinded comparison of daily or weekly hydroxychloroquine versus placebo for 8 weeks. The randomization will be stratified by enrolling site and high- vs. low- risk category, where the high-risk category will consist of HCWs who work in COVID-19 care areas.

A fourth non-randomized comparator group comprised of study participants who are already currently on standard HCQ therapy for an autoimmune disease(s) will be used to assess the impact of weight-based daily dosing of HCQ as compared to the randomized arms.

The trial will use a pragmatic, adaptive enrichment design, in which the primary efficacy analysis will be based on all randomized patients with a negative screen for COVID-19 at baseline, whereas the safety analysis will be based on all randomized patients, including those who are later determined to have been positive for COVID-19 at baseline (given that there may be a time lag to get initial screening COVID-19 test results back after study enrollment).

The trial is designed to have one interim look—when 50% of subjects have completed the study and primary endpoint assessment—for an early treatment efficacy assessment, and possible reassessment of study sample-size if the estimation of placebo infection rate is inadequate.

6.2 Locking Data for Analysis/Transfer

Data will be locked (frozen) for each planned data transfer/ formal data analysis. After the last patient's data/ specimens are collected and all data discrepancies are resolved or closed, data can be locked. The final data analysis/ transfer will be completed within 30 days after the last patient's data/ specimen collection. The data transfer process includes documentation of the database structure, data dictionary with details regarding data element names, labels, formats, and distribution, as well as documentation regarding data collection details, as needed.

6.3 Study Aims, Hypothesis and Proposed Analysis

6.3.1 Primary Aim and Hypothesis

As noted below, the primary aim has been changed to: (based on Study Protocol dated 05/26/2020)

To determine if the use of hydroxychloroquine as preventive therapy decreases the rate of acquisition of SARS-CoV 2 infections [with clinical COVID-19 disease](#) in Study Participants [for each randomized treatment arm](#) as compared to placebo.

From: (based on original Study Protocol, dated at and after 04/06/2020)

To determine if the use of hydroxychloroquine as preventive therapy decreases the rate of acquisition of SARS-CoV 2 infections in Study Participants as compared to placebo.

Primary Hypothesis (P1): Hydroxychloroquine administered daily decreases the rate of acquisition of SARS-CoV 2 infections with clinical COVID-19 disease, compared to placebo; and hydroxychloroquine administered weekly decreases the rate of acquisition of SARS-CoV 2 infections with clinical COVID-19 disease, compared to placebo.

The **primary outcome** will be defined as clinical COVID-19 disease with laboratory confirmation of infection.

Presentation with COVID-19 symptoms during study follow-up (defined as fever $\geq 38^{\circ}$ C, or two or more non-fever symptoms that are new since the baseline) will refer participants to obtain SARS-CoV 2 testing through employee health or participants' primary care physician, with test results documented in their medical record.

Laboratory confirmation of SARS-CoV 2 infection (SARS-CoV 2 test positive) will be defined as at least one positive RT PCR, or both IgM and IgG positive serology. The lab test results can be obtained from (a) study blood samples (IgM and IgG serology), and (b) RT PCR test results ordered by a participant's primary care physician or through employee health.

All participants who test SARS-CoV 2 positive will be followed for at least 30 days after the first positive test for presentation of symptoms.

6.3.2 Full Analysis Set (FAS)

All randomized subjects who do not have a SARS-CoV 2 positive test at the baseline, have taken at least one dose of study medication and provide at least one post-baseline follow-up during the 8-week treatment period. Participants will be analyzed according to the treatment group to which they were assigned according to Intention to treat (ITT).

6.3.3 Safety Analysis Set:

The safety analysis set will consist of all subjects randomized who receive at least one dose of study medication.

6.3.4. Proposed Analysis

6.3.4.1 General Statistical Consideration:

The statistical software package SAS® Version 9.4 or higher (SAS Institute, Cary, NC, USA) will be used to perform all analyses and to summarize data.

The analyses described in this statistical analysis plan (SAP) are considered a priori, in that they have been defined prior to database lock. Any analyses not described herein performed subsequent to database lock will be considered post hoc and exploratory.

6.3.4.2. Handling of missing data:

For summary statistics, results will be reported based upon observed data. The study will make all possible efforts to obtain patient's follow-up data and laboratory confirmation of infection for COVID 19 disease determination. The efficacy analysis will be performed based on all observed data assuming missing as random (MAR), two selected imputation approaches are specified for the sensitivity analysis.

6.3.4.3 Primary Efficacy Analysis.

The FAS is considered. Chi-square test will be used to compare the rate of COVID-19 disease in each randomized treatment group to that of the placebo group using Dunnett's step-up method to adjust for multiple comparisons and controlling for type I error^{1,2}. Specifically, Dunnett's step-up method uses a closed gatekeeping strategy, in which the largest p value will be evaluated first at critical value of 0.05; if that fails, the second p value will be evaluated at critical value of 0.0262 (details in the sample size /power calculation section). A treatment efficacy is detected if the largest p value <0.05 or the second p value <0.0262 . The results of

efficacy analysis will be validated through two specified imputation approaches described in below

Sensitivity Analysis #1: A Tipping Point Analysis (TPA) with delta-adjusting imputation

The primary analyses for COVID 19 disease is based on the observed data and the results are valid if the missing data are missing at random (MAR), meaning that the probability of a value being missing, conditional on the observed data and factors in the statistical model, is random and not dependent on the unknown value of the missing data point.

To address this, we will conduct Tipping Point Analysis (TPA) under the condition of missing not at random (MNAR) to assess the robustness of the primary analysis. Specifically, the TPA first step (STEP 1) is to conduct m (e.g., $m=5$ or 10) multiple imputation (MI) based on baseline covariates, and the prior to 8-week and post-baseline covariates to estimate the missing primary binary endpoint (D) with the underlying assumption of MAR. We will use the Markov Chain Monte Carlo (MCMC) algorithm based on the assumption of multivariate normality (Schafer 1997, Allison 2001) for estimating the mean of D (Allison 2017) stratified by treatment group without rounding to binary values. However, this approach is still under the MAR assumption and hence the result will be further examined by shifting the imputed mean of D in a range of negative to positive values, which can be done by inflecting or suppressing the mean of D among those who had missing D in treated group. A tipping point is identified if it reverses the study conclusion. Those results will be further evaluated on whether the imputed value associated with the tipping point is plausible. SAS Procedures PROC MI and PROC MIANALYZE and SAS %midata macro can be used for TAP analysis.

Sensitivity Analysis #2: A control-based MI

For the most conservative approach, MI can be restricted using data only from the placebo group for the missing endpoint D in both the treated and placebo groups using a similar approach described above for the sensitivity analysis #1 with the shift=0 (the first step).

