### **6.3 Participant Discontinuation**

Participants may discontinue their participation in the study at any time. A Participant may be withdrawn from the study at any time at the discretion of the Investigator. Participants withdrawn from the study prior to randomization will not be included in the study. Using the intention to treat (ITT) approach, participants randomized but not completing the study will be included in the study analyses based on the treatment they were assigned and worse case (test positive) will be considered for those who withdraw early and clinical COVID-19 disease status cannot be confirmed.

For this study, Participants may be discontinued from the randomized study drug if deemed to have developed a study drug related SAE. Safety follow up for up to 4 weeks after discontinuation will be done to determine clinical outcomes via direct communication with the Participant. Similarly, Participants who discontinue medications will be approached to assess any clinical outcomes during their planned 8 study week participation. Participants that are

discontinued from the study by the Investigator, are lost to follow up or decline further study involvement and withdraw their consent will not be approached after study discontinuation.

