### **7.3 SAMPLE COLLECTION AND HANDLING**

Five (5) 10 ml blood tubes consisting of 4 EDTA and 1 Shield tubes of whole blood will be collected from each participant at the baseline/enrollment, week 4 and week 8 timepoints. The samples will be collected using standard aseptic procedures and will be stored in a 4°C refrigerator or cooler until transport to the research laboratory where the samples will be processed. Samples will be processed to serum plasma or cell components. Testing for SARS-CoV 2 will be done for study entry samples. Remainder of the samples will be stored in -80°C for whole blood/serum plasma and cell samples will be stored in liquid nitrogen for future testing.

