#### PATIENT COUNSELING

Counsel Participants that side effects of this medication may include vertigo, tinnitus, visual field defects, color vision abnormalities, nausea, vomiting, fatigue, decreased appetite, headaches, dizziness, and irritability. Participants taking antidiabetic medications will be counseled on the

risk of hypoglycemia and the associated symptoms. Symptoms of toxicity (e.g. rash, visual changes) should be reported to a healthcare provider and to the investigators. Participants will be made aware of the need to keep their study medications out of the reach of children.

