6.3.4.4 Secondary Aims, Hypotheses and Analyses

S1: To compare the rates of SARS-CoV 2 infection status between the randomized treatment arms and the control arms to determine the effect of HCQ dose in the prevention of COVID-19 viremia and disease.

Secondary Hypothesis (S1): There is a hydroxychloroquine dose effect on acquisition of SARS-CoV 2 infection status, compared to placebo.

The endpoint will be SARS-CoV 2 infection status, defined as 1) no SARS-CoV 2 test positive during study follow up; 2) SARS-CoV 2 test positive (i.e., at least one positive RT PCR, or both IgM and IgG positive serology) without clinical symptoms (“asymptomatic SARS-CoV 2 test positive”) 3) SARS-CoV 2 test positive with clinical symptoms (“symptomatic SARS-CoV 2 test positive”).

The analysis will be conducted using FAS. Ordinal logistic regression will be used and analysis will start testing the overall daily and weekly dose effect, followed by pairwise/subgroup comparisons if an overall dose effect is detected at 0.05 level.

S2: To compare the rates of SARS-CoV 2 infection status in the non-randomized comparator arm to the randomized groups to assess the impact of chronic weight-based dosing of HCQ for COVID-19 prevention.

Secondary Hypothesis (S2): There is weekly /daily HCQ dose effect on acquisition of SARS-CoV 2 infection, compared to patients who were already on HCQ.

The endpoint will be the same as described for S1. The analysis will include all randomized *in FAS and non-randomized study participants with at least one post-baseline follow-up.*

We will first test for treatment selection bias using the data collected at the baseline. Inverse probability treatment weighting (IPTW)/propensity score, or matched sub-cohort will be considered to adjust for imbalanced participant characteristics. A similar analysis to that of S1 will be used for testing hypothesis S2.

S3: To compare the rate of SARS-CoV 2 infections as measured by serum IgM/IgG in participants receiving HCQ versus placebo.

Secondary Hypothesis (S3): There is weekly /daily dose effect on status of SARS-CoV 2 infection as measured by serum IgM/IgG, compared to placebo.

The endpoint will be serum IgG/IgM status at each participant’s study conclusion, classified as:

1. Negative (consistently negative for both serologies)
2. Indeterminate (IgM positive, with IgG consistently negative)
3. Positive (IgM and IgG positive, or IgG positive)

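### The protocol counts early withdrawals with unconfirmable COVID-19 status as cases, while the SAP's primary analysis uses observed data, neither keeps nor retires that rule, and drops the protocol's stratification from the primary test

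*SAP*

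**What the plan says.** **Early withdrawals.** Protocol 6.3 (Participant Discontinuation) keeps randomised non-completers under intention to treat and adds: "worse case (test positive) will be considered for those who withdraw early and clinical COVID-19 disease status cannot be confirmed". It does not label this a sensitivity analysis, and the protocol gives no other rule for a missing outcome.

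SAP 6.3.4.2 says: "The efficacy analysis will be performed based on all observed data assuming missing as random (MAR". Two sensitivity analyses follow in SAP 6.3.4.3. One is a tipping-point analysis that shifts imputed values in the treated group; the other is multiple imputation from the placebo arm. Neither is the protocol's rule. SAP 6.3.4.1 adds: "Any analyses not described herein performed subsequent to database lock will be considered post hoc and exploratory".

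**Who is analysed.** SAP 6.3.2 limits the full analysis set (FAS) to baseline-negative participants who "have taken at least one dose of study medication and provide at least one post-baseline follow-up during the 8-week treatment period". The protocol's intention-to-treat wording would keep some of the people whom this removes.

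**The test.** Protocol 8.3 specifies a Mantel-Haenszel chi-square stratified by site and high or low risk, the randomisation strata. SAP 6.1 names the same strata for randomisation, but SAP 6.3.4.3 describes the primary test only as a chi-square.

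**When the outcome is missing.** SAP 6.3.1 requires clinical disease with laboratory confirmation but does not say when that outcome counts as missing. The nearest text is category 1 of secondary endpoint S1: "no SARS-CoV 2 test positive during study follow up".

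**The concern.** A participant who leaves early with unknown status is a case under one document and contributes no outcome under the other. The SAP flags its change of primary aim and of power calculation, but not this change. Read with SAP 6.3.4.1, a rule that the protocol pre-specified becomes post hoc without a recorded decision.

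The choice can change the result. Counting unknowns as cases adds the same non-informative events to every arm and dilutes a true effect. If unknown status is more or less common on HCQ than on placebo, the rule biases the comparison in either direction. If the choice is still open at unblinding, it could be made with the results in view.

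The strata are a smaller matter: the protocol's primary test and the SAP's do not match as written.

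**Working it through.** **Inputs.** Rates of 10% on placebo and 6.8% on each HCQ arm, and 900 or 935 per arm (SAP 6.4). Two-sided step-up at the final look: both arms are declared if the larger p < 0.05; otherwise the arm with the smaller p is declared if it is < 0.0262 (SAP 6.3.4.3). The share w with unknown status is **assumed**. The 5-10% in Protocol 8.3 and SAP 6.4 is an allowance for baseline positives or FAS exclusions, not a value of w.

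**Method.** 400,000 simulated trials per scenario, Pearson chi-square of each HCQ arm against the shared placebo arm, unknown status independent of outcome. Power means that at least one HCQ arm is declared.

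- Observed data: rate p on about n(1 − w) people.
- Protocol rule: rate w + (1 − w)p on all n.

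**The SAP's own figure.** With w = 0 and 10% vs 6.8%, I get 0.781 at 935 per arm (SAP Table 1: 0.800) and 0.764 at 900 (SAP: 0.770). For 10% vs 7.3% and 6.3%, I get 0.815 at 935 (SAP: 0.811) and 0.798 at 900 (SAP: 0.800). Agreement is within 2 points. The interim look adds less than 0.001, so it is left out below.

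**Equal unknown rates, 935 per arm**

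| w | Rates under protocol rule | Relative reduction | Power, observed data | Power, protocol rule |
|---|---|---|---|---|
| 2% | 11.8% vs 8.7% | 27% | 77% | 69% |
| 5% | 14.5% vs 11.5% | 21% | 76% | 57% |
| 10% | 19.0% vs 16.1% | 15% | 73-74% | 43% |

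For example, at w = 5%: 0.05 + 0.95 × 0.10 = 0.145; 0.05 + 0.95 × 0.068 = 0.1146; 1 − 0.1146/0.145 = 0.21.

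**Unequal unknown rates, no drug effect, 900 per arm, placebo w = 5%.** The placebo rate under the rule is 14.5%.

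| w on both HCQ arms | HCQ rate under rule | False efficacy | False harm |
|---|---|---|---|
| 3% | 12.7% | 23% | 0.1% |
| 4% | 13.6% | 9% | 0.5% |
| 6% | 15.4% | 0.6% | 8% |
| 8% | 17.2% | <0.1% | 40% |

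On observed data the error stays at 5% in total, 2.5% each way, in every row. With the planned effect present and 5% unknown on placebo, the rule gives 94% power if both HCQ arms have 3% unknown and 4% if both have 8%.

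**One data set, both rules.** One HCQ arm against placebo, 935 per arm.

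- 5% unknown in each arm (47 people). Observed: 89/888 vs 60/888, p = 0.013. Protocol rule: 136/935 vs 107/935. The pooled rate is 243/1870 = 0.130, the difference 0.0310, the standard error √(0.130 × 0.870 × 2/935) = 0.01555, so z = 1.99 and p = 0.046. That passes 0.05 and fails 0.0262.
- 5% unknown on placebo, 8% on HCQ (47 and 75 people). Observed: 89/888 vs 58/860, p = 0.014. Protocol rule: 136/935 vs 133/935, p = 0.84.

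**Strata.** One comparison, 900 per arm, two equal strata (assumed), 32% reduction in each, no continuity correction.

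| Placebo risk by stratum | Power, plain | Power, stratified | Type I error, plain |
|---|---|---|---|
| 12% / 8% | 68.9% | 69.0% | 0.049 |
| 15% / 5% | 69.2% | 70.0% | 0.046 |
| 18% / 2% | 69.5% | 71.5% | 0.042 |

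The stratified test holds type I error at about 0.050. The gain is 0.1 to 2.0 points.

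**The case against.** **The conflict may come from the document versions.** The SAP cites a protocol dated 05/26/2020 and describes a wider population than the supplied protocol. A version not supplied may have dropped the rule. This stands as a limit. It would not fill the SAP's own gaps on strata and on when the outcome is missing.

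**This is reconciliation, not a flawed analysis.** That is largely right. The SAP's observed-data primary is the better of the two, and the power losses above belong to the rule to be retired. For an efficacy claim the SAP's tipping point is already harsher at its extreme: with unknowns on HCQ counted as cases and placebo left as observed, none of 400,000 trials at 2%, 5% or 10% unknown stayed positive while the protocol rule was negative. Keeping the rule as a sensitivity analysis is useful mainly because it covers people outside the FAS and leaves a record.

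**Silence on strata need not repeal Protocol 8.3.** SAP section 6 says that the SAP takes up issues the protocol leaves open, and Mantel-Haenszel is itself a chi-square test. That is fair, but one phrase removes the doubt.

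**A stronger reading is tempting: that untested participants would be dropped and HCQ made to look protective.** Testing follows symptoms: "two or more non-fever symptoms that are new since the baseline) will refer participants to obtain SARS-CoV 2 testing". Protocol 7.3 commits only to this: "Testing for SARS-CoV 2 will be done for study entry samples". The HCQ effects listed for counselling ("nausea, vomiting, fatigue, decreased appetite, headaches, dizziness, and irritability") overlap with the COVID-19 symptoms in Protocol 6.2.1, so testing could differ by arm. The documents do not support going that far:

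- End-of-study serology is planned (Protocol 2.4, endpoints 3 and 4; Protocol 4; SAP S3 and S4).
- S1 category 1 requires only the absence of a positive test.
- The SAP powers the trial on about 935 analysed of 1,000 per arm, which dropping large numbers of untested people would contradict.
- Even if untested non-cases were dropped, assumed testing of 90% on placebo and 92% on HCQ gives 3.5% false efficacy against 2.5% nominal.
- The direction is not settled either, because extra testing may also find silent infections.

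What remains is a missing definition.

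**Conclusion.** The point holds as a conflict between the two documents, and it should be fixed.

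1. **Early withdrawals.** This is the substantive part. Protocol 6.3 and SAP 6.3.4.2 treat the same people differently, and the difference can reverse the primary conclusion. The size depends wholly on assumed unknown rates. The 5% error for observed data also assumes that unknown status is unrelated to outcome.
2. **Strata.** This is minor: 0 to 2 points of power. A reader might infer that the unstratified test is invalid. It is not; it is slightly conservative.
3. **Definition of missing.** This is a clarification only.

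A reader might also infer that the sponsor dropped the rule deliberately or without approval. The documents cannot show that, because the protocol version cited by the SAP was not supplied.

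**What to change.** - **Protocol 6.3:** remove the test-positive rule from the primary analysis and refer to SAP 6.3.4.2. Leave the intention-to-treat wording as it is.
- **SAP 6.3.4.3, sensitivity analysis:** add the rule as a third named sensitivity analysis. Apply it to all randomised baseline-negative participants, including those the FAS drops, with early withdrawals of unconfirmable status counted as cases in every arm.
- **SAP 6.3.4.3, primary test:** name the Mantel-Haenszel chi-square stratified by site and risk group, with a pre-set rule for pooling very small sites.
- **SAP 6.3.4.2, definition:** state three things.
  - A participant followed to the end without qualifying symptoms is a non-case, tested or not.
  - An asymptomatic positive is a non-case for the primary outcome unless symptoms appear in the 30-day follow-up of SAP 6.3.1. This has to be explicit, because Protocol 4 ends participation at a positive test, and a loose definition would make such people missing.
  - Missing means that follow-up ended early with no positive test and no event, or that qualifying symptoms have no PCR or serology result.
- **Reporting:** give unknown status and FAS exclusions by arm.
- **Timing:** record the decisions, with dates, before unblinding.

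The cost is wording in two documents and no new data. If the 05/26/2020 protocol or a later one has already retired the rule, only the SAP edits remain.
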